2.2. Specific Objectives

- To determine the effectiveness of Tenofovir Emtricitabine in addition to the use of Personal Protective Equipment (PPE) for the prevention of SARS-CoV-2 infection in health care personnel caring for patients with confirmed or suspected COVID-19 in the emergency room, general ward and ICU.
- To evaluate the safety (adverse events frequency) of Tenofovir Emtricitabine in addition to the use of Personal Protective Equipment (PPE) for the prevention of SARS-CoV-2 infection in health care personnel caring for patients with confirmed or suspected COVID-19 in the emergency room, general ward and ICU.
- To evaluate the adherence to Tenofovir Emtricitabine of health care personnel caring for patients with confirmed or suspected COVID-19 in the emergency room, general ward, and ICU.
- To determine the frequency of discontinuation for any reason of Tenofovir Emtricitabine in health care personnel caring for patients with confirmed or suspected COVID-19 in the emergency room, general ward, and ICU.
- To describe and compare the clinical course and severity of participants who develop COVID-19 in the intervention and control groups.

3. Methodology

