3.3. Result and primary Outcome

Primary Outcome

✓ SARS-CoV-2 infection defined as:

- Detection of SARS-CoV-2 nucleic acid using RT-PCR in any of the specimens collected during the study-follow-up including the asymptomatic participant

-Positive IgG antibodies against SARS-CoV-2 in any of the specimens collected during the study-follow-up

Secondary outcomes

- Serious and non-serious adverse events

- Discontinuation of using the intervention (TDF/FTC or placebo) for any reason

- Adherence to TDF/FTC defined as: number of tablets taken/total number of dispensed tablets

- Severity of SARS-CoV-2 infections according to the following categories:

[figure not shown]
- Asymptomatic infection.

- Mild symptomatic SARS-CoV-2 infection with no need for hospitalization.

- Moderate symptomatic SARS-CoV-2 infection that requires hospitalization, but no ICU.

- Severe SARS-CoV-2 infection: dyspnea with other SARS-CoV-2 symptoms requiring ICU hospitalization.

Graph 1. Flowchart of assignments and follow up of the clinical trial.

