3.6.5. Administration of the intervention product and placebo

Volunteers assigned to the intervention group will receive one tablet of TDF/FTC 300/200mg each day. Each volunteer will be given 60 tablets of the medicine at the beginning of the treatment and its administration will be verified daily by sending a virtual survey, in which the subject answers if he took the intervention, plus a follow-up diary that will be given to the patient of Virtual or manual way for people without access, to write adverse events, as well as the hours of daily exposure to patients with suspected or diagnosed COVID 19 and adherence to personal protection elements. These data will be stored in an eCRF for clinical follow-up, adverse events, and adherence.

Patients assigned to the control group will receive a placebo that will have the same appearance and size and will not have any active ingredients. Similarly, 60 placebos will be delivered from the start of treatment.

The medicine must be stored at a temperature not exceeding 30 ° C and in an environment without excessive humidity in its authorized container and packaging.

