3.6.9. Procedure in case of presenting the primary outcome

If the volunteer, after the start of the study, has a positive result of RT-PCR or IgG for SARS CoV2, which confirms the infection by COVID 19, they will be contacted virtually or in person. During this intervention, the following actions will be carried out:

- You will be given information about your result, and you will be instructed to contact your occupational risk and health insurer.
- The presence of alarm signs (drowsiness, dyspnea, cyanosis) will be evaluated. In case of any of these symptoms are present, the patient will be instructed to attend the emergency service, to receive treatment in accordance with current national and institutional guidelines.
- The volunteer will be instructed to suspend the intervention product, and the masking will be released.
- National Public Health Surveillance System mandatory notification form will be filled out, the institution where the volunteer works will be informed, and the completed form will be sent.

- The volunteer will be informed that telephone follow-up will be carried out every 5 days until the symptoms are resolved or a maximum of six weeks after the diagnosis of COVID 19. In case of presenting any alarm sign during the follow-up, the patient will be recommended to attend the emergency department.

During the telephone follow-up, the volunteer's primary outcome (COVID 19 infection) will be classified as follows: asymptomatic, mild, moderate, or severe COVID. If the patient does not answer due to physical impossibility (e.g. intubation), communication with a companion or family member previously authorized by the patient will be sought.

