The hazard ratio will be estimated by comparing the risk of infection in the intervention group (TDF/FTC + EPP), with the risk in the control group (placebo + EPP), with a confidence interval of 95 %, using a univariate Cox regression model.

If necessary, adjustment will be made for variables that may affect the occurrence of the primary outcome and that are not balanced between the intervention group and the placebo group; The need for adjustment with an OR greater than 1.5 will be considered for dichotomous categorical

variables, such as sex; or if there are differences between the groups greater than 0.25 of the standard deviation for continuous variables such as age, adherence to pharmacological intervention or EPP, and hours of exposure to the COVID area. For the calculation of the adjusted hazard ratio, a multivariate Cox proportional hazards model will be used, if the proportionality assumption is met, or an extended Cox model if this assumption is not met.

For secondary outcomes

-The proportion of incidence of total adverse effects in each group will be determined at day 60 after randomization, estimated as the cumulative incidence using the Kaplan Meier method.

The hazard ratio ("Hazard Ratio") will be estimated by comparing the risk of adverse events in the intervention group (TDF/FTC + EPP), with the risk in the control group (placebo + EPP), with a confidence interval of 95%, using a univariate Cox regression model.

Additionally, the same analysis will be performed for serious adverse events.

- The proportion of incidence of discontinuation of the intervention in each group, for any reason, will be determined at day 60 after randomization, estimated as the cumulative incidence using the Kaplan Meier method.

The hazard ratio will be estimated by comparing the discontinuation of the intervention in the intervention group (TDF/FTC + EPP), with the risk in the control group (placebo + EPP), with a confidence interval of 95 %, using a univariate Cox regression model.

- It will be determined as the difference in the mean or median (according to the distribution of the data) of the percentage in which the individuals were adherent

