Gallant JE et al. In a randomized clinical trial comparing efavirenz (EFV) plus TDF/FTC (N = 257) vs EFV plus zidovudine (AZT) / lamivudine (3TC) (N = 254) for the management of HIV infection in 511 Subjects over 18 years of age, for 144 weeks, reported the following adverse reactions: dizziness (8%), diarrhea (7%), nausea (8%), fatigue (7%), headache (5%), depression (4%), insomnia (4%), skin rash (5%) (93).

Reported laboratory abnormalities included: amylase greater than or equal to 132 (17%), triglycerides greater than 400 mg / dL (13%), neutrophils less than 1000 (7%), hematuria (9%), AST greater than 109 in men or 86 in women (8%), ALT greater than 91IU / L in men or 86 IU / mL in women (7%) (93). However, in this study TDF/FTC was accompanied by EFV, which explains several of the adverse effects, especially psychiatric ones, and skin rash.

More recently, the safety and risk profile of TDF/FTC adverse reactions has been studied in clinical studies of HIV pre-exposure prophylaxis (PrEP) in monotherapy. Grohskopf A. et al. Conducted a clinical experiment to evaluate the safety of a daily dose of TDF in HIV-uninfected subjects for 24 months. The study drug was initiated by 373 (93%) volunteers (186 TDF and 187 placebo), of whom 325 (87%) completed the final study visit. Of 2428 adverse effects (AE) reported among 334 (90%) volunteers, 2366 (97%) were of mild or moderate severity. The frequencies of commonly reported AE did not differ significantly between the TDF and placebo arms. In multivariate analyzes, back pain was more likely among TDF recipients (P = 0.04), these reports were not associated with documented fractures or other objective findings. There was no grade ≥ 3 creatinine elevations, and grade 1 and 2 creatinine elevation were not associated with TDF reception. The estimated percentage of adherence was 92% per pill count. (94).

The Partners PrEP study recruited 4,758 couples, of which 4,747 were followed, 1,584 randomly assigned to TDF, 1,579 to TDF-FTC, and 1,584 to placebo. The rate of serious adverse events at 36

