months of follow-up was similar in all study groups. There were no statistically significant differences in the frequency of deaths, serious adverse events, or serum creatinine and phosphorus abnormalities in the study arms. Neutropenia was seen more frequently in the TDF/FTC arm (15% with a grade 1 or 2 event, 4% with a grade 3 or 4 event), but not in the TDF arm (12% with a grade 1/2, 2% grade 3/4), compared to placebo (12% grade 1/2, 2% grade 3/4). The study medication was well tolerated, with a moderate increase in reports of gastrointestinal side effects and fatigue in the two active arms compared to the placebo arm, mainly during the first month of administration (77,95)

Retention was 96% or greater during the study period. Study medication interruptions for safety-related reasons accounted for less than 1% of the total follow-up time: 0.6% in the TDF group, 0.7% in the TDF-FTC group, and 0.6% in the placebo group. (77.95)

The iPrEX study enrolled 1603 volunteers, of whom 1,225 chose to take PrEP. Reported symptoms peaked in the first month, with 39% potentially related to PrEP compared to 22% at baseline. Symptoms largely resolved within 3 months. Symptoms related to the digestive tract in the first 4 weeks were inversely associated with adherence at 4 weeks (OR = 0.47, 95% CI 0.23 to 0.96). Reports of gastrointestinal symptoms were associated with 7% (95% CI, 4% -11%) of suboptimal adherence in this cohort (96).

In this study, PrEP delivery was discontinued during the study in 56 (5%) volunteers due to "adverse effects." The study volunteer or medical staff could initiate interruptions. The interruption was temporary for 22 volunteers, the combined duration of these temporary interruptions totaled 10 person-years, a reduction of 0.6% (10 person-years from a possible 1784 person-years) in the total possible person-years. The discontinuation was permanent for 34 volunteers and decreased the total possible use of PrEP in 35 person years, 2.9% of the possible use in the cohort. The most common adverse effects cited for non-dispensing were nausea, abdominal pain (0.9% possible use), diarrhea (0.4%), and skin problems / itching, pain in head and flatulence (0.3% each (96).

- Laboratory abnormalities

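### The adherence comparison leaves mean or median to be chosen after the data are seen, and the median difference can be a structural zero if more than half of each arm takes every tablet

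*Combined protocol and SAP*

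**What the plan says.** Adherence is a specific objective in section 2.2 ("To evaluate the adherence to Tenofovir Emtricitabine of health care personnel caring for patients") and a secondary outcome in section 3.3: "Adherence to TDF/FTC defined as: number of tablets taken/total number of dispensed tablets". Section 3.6.5 fixes the denominator: "Each volunteer will be given 60 tablets of the medicine at the beginning of the treatment", with the same number for placebo.

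Section 4, under secondary outcomes, gives adherence a single line: the "difference in the mean or median (according to the distribution of the data) of the percentage in which the individuals were adherent". It states no rule for choosing between the two measures, no confidence interval, no test and no threshold. The neighbouring outcomes are treated more fully. Adverse events and discontinuation each get a Kaplan-Meier estimate at day 60 and a hazard ratio with a 95% interval.

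Two background statements in section 5.1.1 bear on what the data may look like. A cited tenofovir trial reports: "The estimated percentage of adherence was 92% per pill count". A cited HIV-prevention cohort reports: "Reports of gastrointestinal symptoms were associated with 7% (95% CI, 4% -11%) of suboptimal adherence in this cohort".

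**The concern.** A ratio of tablets taken to tablets dispensed has a ceiling at 100%. At high adherence it is likely to be left-skewed, and a choice made by looking at the distribution would then tend towards the median. A median sitting at the ceiling carries no information about the people below it. If tolerability makes a minority on active drug skip doses, the loss lies in the lower tail, and a difference in medians may not move.

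At stake is the between-arm answer to one stated objective, and a figure readers would use to judge whether the primary result was diluted by missed doses. A reported difference of zero could be read as equal adherence when it only reflects the ceiling. Choosing the summary after seeing the data adds an avoidable analyst decision.

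**Working it through.** **The plan's own figures.** The documents give no numerical target for adherence. The only planning figures used here are the infection risks of 0.10 and 0.05 in section 3.4. They do underlie the stated sample size: with two-sided alpha 0.05 and power 0.80, n per arm = [1.96√(2×0.075×0.925) + 0.8416√(0.09+0.0475)]² / 0.05² = 435, against 429 stated.

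**1. When both medians reach the ceiling.** One tablet is 1/60 = 1.67 points. An arm's median is 100% when more than half of the arm takes 60 of 60. If days were missed independently with probability m, this needs (1−m)^60 > 0.5, so m below about 1.15%. The documents do not say which side of this line the trial will fall on. The cited 92% fits either side:
- 60% at full adherence and the rest averaging 80% gives 0.6×100 + 0.4×80 = 92.
- Independent omission of 8% of days also gives a mean of 92, but a median of 55/60 = 91.7%.

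**2. Illustration across a range of full adherence.** All distributions are assumptions: 475 per arm; a share p of placebo takes every tablet; the rest follow a Beta(6, 1.5) distribution (mean 6/7.5 = 80%), rounded to whole tablets; in the active arm, 7% are replaced by people taking a uniform 20-80% (mean 50%). Then:
- placebo mean = 100p + 80(1−p)
- active share at full adherence ≈ 0.93p
- mean difference = 0.07 × (placebo mean − 50)

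| p (placebo) | Active share full | Mean difference, points | Simulated trials with median difference exactly 0 |
|---|---|---|---|
| 40% | 37% | 0.07×38 = 2.7 | 22% |
| 45% | 42% | 0.07×39 = 2.7 | 18% |
| 50% | 47% | 0.07×40 = 2.8 | 15% |
| 55% | 51% | 0.07×41 = 2.9 | 74% |
| 60% | 56% | 0.07×42 = 2.9 | 99% |
| 70% | 65% | 0.07×44 = 3.1 | 100% |

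The last column comes from 1,500 trials per row. At 40%, 45% and 50% the median difference averages 1.9, 2.3 and 2.6 points, so there the median does register the drop. The switch comes where 0.93p = 0.5, that is p ≈ 54%.

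A second set of assumed distributions (429 per arm, 1,000 trials each) gives the same pattern. With 80% versus 73% fully adherent (placebo versus active), the median difference is 0 in every trial while means differ by 3.6 points. With 55% versus 48%, it is 0 in 18% of trials and averages 2.3 points.

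**3. The mean needs a different denominator.** On a positive test, section 3.6.9 states: "The volunteer will be instructed to suspend the intervention product, and the masking will be released". The 60 dispensed tablets stay in the denominator. Let f be the average unused fraction among infected participants, and take the 92% mean as the base. With no drug effect on adherence at all:
- placebo loses 0.10 × f × 92 points and active loses 0.05 × f × 92
- spurious placebo deficit = 4.6f points: 2.3 at f = 0.5 and 1.2 at f = 0.25

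Infections found at the day-60 RT-PCR or the day-75 IgG leave no tablets unused, so f may well be below 0.5. With uniformly timed stopping (f = 0.5), simulation finds this spurious deficit significant in about 45% of trials.

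Now add the step 2 drug effect at p = 60%. Placebo is 92 × (1−0.05) = 87.4. Active is (92−2.94) × (1−0.025) = 86.8. The true gap of about 2.9 points shrinks to about 0.6.

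**The case against.** The strongest reply is that the zero rests on an unknown input. No section states or implies that more than half of each arm will take all 60 tablets, and with 40-50% fully adherent the median works tolerably. That stands, and it is why the point is conditional.

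A reader might infer that the plan prescribes the median. It does not: the mean is equally permitted. What can be criticised is that the choice is left open.

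A reader might also take the cited 7% as an extra 7% of participants becoming non-adherent. The sentence in section 5.1.1 more naturally describes a share of suboptimal adherence. If 40% of participants are below full adherence, 7% of that is 2.8% of participants, and the mean difference falls to 0.028×42 = 1.2 points. The power of a mean comparison in step 2's setting at p = 60% is then about 23%, compared with about 85% if the 7% are all extra participants. Neither is a property of this trial.

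Nor do the documents support the inference that a tolerability problem would be hidden. Adverse events get their own time-to-event analysis, and so does stopping: "The proportion of incidence of discontinuation of the intervention in each group, for any reason, will be determined at day 60". Appendix 3 records interruptions, their length and their cause. Section 4 also promises measures of dispersion in its descriptive phase. In the 60% setting the lower quartiles differ by nearly 5 points, so reported quartiles would show the drop.

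What survives is narrower. Skipped doses without stopping are compared between arms through the adherence outcome, and its one comparative summary is unfixed, has no interval and can be uninformative.

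**Conclusion.** The point holds in conditional form. The choice between mean and median is open until the data are seen, and no interval is planned. The ceiling at 100% follows from the definition and the 60-tablet supply. If more than half of each arm takes every tablet, a median difference of 0 is guaranteed whatever happens below the ceiling; under the illustrative assumptions the mean would then differ by about 3 points. Below about half, the median does move. The share taking every tablet is an assumption, so results should be read across the 40-70% range and not as one zero rate.

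Switching to the mean alone is not enough. With dispensed tablets as denominator, the trial's own planned infection difference biases the comparison by 4.6f points, or 2.3 if half the tablets go unused, in the direction that masks lower adherence on active drug.

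This is a minor point about one secondary outcome. The primary analysis and the sample size are untouched.

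**What to change.** In section 4, replace the adherence line with:
- **Main comparison.** Between-arm difference in mean adherence with a bootstrap or large-sample 95% CI, whatever the distribution.
- **Lower tail.** Difference in the proportion of participants below one adherence cut-off, fixed in the SAP before unblinding, with a 95% CI.
- **Description only.** Medians and quartiles by arm.
- **Denominator for this comparison.** Tablets due up to infection or protocol-required suspension. State which withdrawal reasons count as required. A participant's own decision to stop should not shorten the denominator, or a tolerability effect would be removed by definition.

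The cost is SAP wording and a little more analysis on a secondary outcome. Appendix 3 already collects tablet counts, interruption days, product-withdrawal dates, positive RT-PCR dates and visit dates. Infection is not among its listed product-withdrawal reasons, so the stop date for infected participants should be taken from the positive result or the visit at which it was found.

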5.1 Risks for volunteers

The risks for volunteers will be divided into those related to the pharmacological intervention.

5.1.1 Risks potentially associated with pharmacological intervention

TDF/FTC is considered a safe drug in the short term, and in periods of up to 2 to 3 years of use (81). In the studies of PrEP in HIV in which this drug is used as monotherapy, the systematic review by Fonner et al. (82) found no differences in the proportion of adverse events comparing TDF/FTC with placebo, in 10 randomized clinical trials (RCTs) controlled (OR 1.01, 95% CI 0.99 to 1.03, $p = 0.27$); It also found no differences in the subgroup analysis, according to adherence, gender, dose or age; nor in grade 3 or 4 adverse events when comparing the PrEP and placebo groups in 11 placebo-controlled RCTs (risk ratio = 1.02, 95% CI 0.92-1.13, $p = 0.76$).

The most common adverse effects reported with the drug are nausea, gastrointestinal (abdominal pain, bloating), and headache (77, 81). The use of TDF-FTC as PrEP has been associated with a mild non-progressive decrease in creatinine clearance (83), which is reversible on discontinuation of the drug (84).

An association has also been described between a decrease in bone mineral density (BMD) and the use of FTC-TDF for 24 weeks (84-87), but no evidence of an increased risk of fractures has been found, on the other hand, change in BMD did not progress after 24 weeks of use and recovered to levels seen in the placebo arm after stopping TDF/FTC (88-89).

Finally, there is a risk of severe acute exacerbations of hepatitis B in patients with hepatitis B virus (HBV) infection who discontinue TDF/FTC. Liver function should be closely monitored with clinical and laboratory follow-up for several months in HBV-infected patients who interrupt TDF/FTC, however, this phenomenon is rare, and the only evidence available is case reports. (90-92). In the present study, this risk will be avoided, because people with acute or chronic hepatitis B infection will be excluded and all volunteers will have immunity to hepatitis B, with anti-HBs greater than 10 IU/ml.

The following information presents, in more detail, the safety of TDF/FTC based on clinical, laboratory abnormalities, as well as alterations in bone mineralization and kidney function.

- Experience based on clinical experiments

Due to the control conditions of clinical trials, it is possible that the rates of adverse reactions that have been described do not necessarily reflect those observed in clinical practice and may be overestimated.

Gallant JE et al. In a randomized clinical trial comparing efavirenz (EFV) plus TDF/FTC (N = 257) vs EFV plus zidovudine (AZT) / lamivudine (3TC) (N = 254) for the management of HIV infection in 511 Subjects over 18 years of age, for 144 weeks, reported the following adverse reactions: dizziness (8%), diarrhea (7%), nausea (8%), fatigue (7%), headache (5%), depression (4%), insomnia (4%), skin rash (5%) (93).

Reported laboratory abnormalities included: amylase greater than or equal to 132 (17%), triglycerides greater than 400 mg / dL (13%), neutrophils less than 1000 (7%), hematuria (9%), AST greater than 109 in men or 86 in women (8%), ALT greater than 91IU / L in men or 86 IU / mL in women (7%) (93). However, in this study TDF/FTC was accompanied by EFV, which explains several of the adverse effects, especially psychiatric ones, and skin rash.

More recently, the safety and risk profile of TDF/FTC adverse reactions has been studied in clinical studies of HIV pre-exposure prophylaxis (PrEP) in monotherapy. Grohskopf A. et al. Conducted a clinical experiment to evaluate the safety of a daily dose of TDF in HIV-uninfected subjects for 24 months. The study drug was initiated by 373 (93%) volunteers (186 TDF and 187 placebo), of whom 325 (87%) completed the final study visit. Of 2428 adverse effects (AE) reported among 334 (90%) volunteers, 2366 (97%) were of mild or moderate severity. The frequencies of commonly reported AE did not differ significantly between the TDF and placebo arms. In multivariate analyzes, back pain was more likely among TDF recipients (P = 0.04), these reports were not associated with documented fractures or other objective findings. There was no grade ≥ 3 creatinine elevations, and grade 1 and 2 creatinine elevation were not associated with TDF reception. The estimated percentage of adherence was 92% per pill count. (94).

The Partners PrEP study recruited 4,758 couples, of which 4,747 were followed, 1,584 randomly assigned to TDF, 1,579 to TDF-FTC, and 1,584 to placebo. The rate of serious adverse events at 36

months of follow-up was similar in all study groups. There were no statistically significant differences in the frequency of deaths, serious adverse events, or serum creatinine and phosphorus abnormalities in the study arms. Neutropenia was seen more frequently in the TDF/FTC arm (15% with a grade 1 or 2 event, 4% with a grade 3 or 4 event), but not in the TDF arm (12% with a grade 1/2, 2% grade 3/4), compared to placebo (12% grade 1/2, 2% grade 3/4). The study medication was well tolerated, with a moderate increase in reports of gastrointestinal side effects and fatigue in the two active arms compared to the placebo arm, mainly during the first month of administration (77,95)

Retention was 96% or greater during the study period. Study medication interruptions for safety-related reasons accounted for less than 1% of the total follow-up time: 0.6% in the TDF group, 0.7% in the TDF-FTC group, and 0.6% in the placebo group. (77.95)

The iPrEX study enrolled 1603 volunteers, of whom 1,225 chose to take PrEP. Reported symptoms peaked in the first month, with 39% potentially related to PrEP compared to 22% at baseline. Symptoms largely resolved within 3 months. Symptoms related to the digestive tract in the first 4 weeks were inversely associated with adherence at 4 weeks (OR = 0.47, 95% CI 0.23 to 0.96). Reports of gastrointestinal symptoms were associated with 7% (95% CI, 4% -11%) of suboptimal adherence in this cohort (96).

In this study, PrEP delivery was discontinued during the study in 56 (5%) volunteers due to "adverse effects." The study volunteer or medical staff could initiate interruptions. The interruption was temporary for 22 volunteers, the combined duration of these temporary interruptions totaled 10 person-years, a reduction of 0.6% (10 person-years from a possible 1784 person-years) in the total possible person-years. The discontinuation was permanent for 34 volunteers and decreased the total possible use of PrEP in 35 person years, 2.9% of the possible use in the cohort. The most common adverse effects cited for non-dispensing were nausea, abdominal pain (0.9% possible use), diarrhea (0.4%), and skin problems / itching, pain in head and flatulence (0.3% each (96).

- Laboratory abnormalities

Grade 2 to 4 laboratory abnormalities seen in the iPrEx and Partners PrEP assays are rare, generally less than 5% (80-82). Six subjects in the TDF-containing arms of the Partners PrEP trial discontinued the trial due to an increase in serum creatinine, compared with no discontinuation in the placebo group. One subject in the TDF/FTC arm of the iPrEx trial discontinued due to an increase in serum creatinine and another subject discontinued due to low serum phosphorus. Grades 2-3 proteinuria (2-4 +) and / or glycosuria (3+) occurred in less than 1% of TDF/FTC-treated subjects in the iPrEx trial and the Partners PrEP trial.

- Alterations in bone mineralization.

In some clinical trials evaluating TDF/FTC in pre-exposure prophylaxis for HIV for 18 months, decreases in bone mineral density (BMD) have been observed and described in uninfected individuals. In the iPrEx trial, a substudy of 503 subjects found mean changes from baseline in BMD

ranging from -0.4% to -1.0% in total hip, spine, femoral neck, and trochanter in the TDF/FTC group compared to the placebo group, who returned to their baseline values after PrEP was discontinued. 13% of TDF/FTC treated subjects, in contrast to 6% of placebo treated subjects, lost at least 5% of BMD in the spine during treatment. Bone fractures were reported in 1.7% of the TDF/FTC group compared to 1.4% in the placebo group, however, no correlation was observed between BMD and fractures. (96)

The Partners PrEP trial found similar fracture rates between the treatment and placebo groups (0.8% and 0.6%, respectively); BMD was not assessed in this trial (81). Liu AY, et al. In 2011 evaluated the prevalence of low BMD using dual energy X-ray absorptiometry (DEXA), in a baseline cohort of 210 HIV-uninfected men who have sex with men (MSM) who underwent a randomized clinical trial of daily TDF versus placebo. At baseline, 20 volunteers (10%) had low BMD (Z score \leq 2.0 at L2-L4 spine, total hip, or femoral neck). Low BMD was associated with the use of amphetamines (OR = 5.86, 95% CI 1.70-20.20) and inhalants (OR = 4.57, 95% CI 1.32-15.81); there was a 1.1% net decrease in mean BMD in the TDF group versus the pretreatment / placebo group in the femoral neck (95% CI 0.4-1.9%), 0.8% net decrease in the total hip (95% CI 0.3-1.3%) and 0.7% in column L2-L4 (95% CI -0.1-1.5%). At 24 months, 13% vs. 6% of volunteers experienced more than 5% loss of BMD at the femoral neck in the TDF versus placebo groups, however these associations were not statistically significant ($p = 0.13$) (87)

Kasonde M, et al. Evaluated the effect on bone mineral density of daily TDF/FTC use compared to placebo among heterosexual men and women aged 18 to 29 years enrolled in the Botswana TDF2 PrEP study. Volunteers had BMD measurements at baseline and then every 6 months with dual-energy X-ray absorptiometry (DEXA) performed on the hip, spine, and forearm. A total of 220 volunteers (108 TDF-FTC, 112 placebo) had baseline BMD measurements at all three anatomical sites; 15 (6.8%) of the volunteers had a low BMD level at baseline (z-score $<$ -2.0 at each anatomical site) including 3/114 women (2.6%) and 12/106 men (11.3%) ($p = 0.02$) (97).

Low baseline BMD was associated with low weight ($p = 0.02$), high blood urea nitrogen content ($p = 0.02$) or high alkaline phosphatase ($p = 0.03$), and low creatinine clearance ($p = 0.04$). BMD losses $>$ 3.0% at any anatomical site at any time after study initiation were significantly greater for the TDF-FTC treatment group [34/68 (50.0%) versus 26/79 (32.9%) placebo ($p = 0.04$). There was a small but significant difference in mean percentage change in BMD from baseline for TDF/FTC versus placebo at all three sites at month 30 [forearm -0.84% ($p = 0.01$), column -1.62% ($p = 0.0002$), hip -1.51% ($p = 0.003$). In conclusion, the use of TDF-FTC was associated with a small but statistically significant decrease in BMD in the forearm, hip and lumbar spine. A high percentage (6.8%) of healthy young adults in Botswana had an abnormal baseline BMD. This association is in relation to the time of exposure to TDF/FTC. (97).

- TDF/FTC and kidney function

Tenofovir-associated nephrotoxicity encompasses a spectrum of manifestations including proximal tubular dysfunction, acute kidney injury, CKD, and nephrogenic diabetes insipidus. Proximal tubular dysfunction is the main one among them, it has to do with the depletion of mitochondrial DNA mediated by the accumulation of drugs within the proximal renal tubules. Proximal tubular dysfunction can rarely progress to Fanconi syndrome, a complete tubulopathy that includes

metabolic acidosis and bone disorders and occurs in 0.3 to 2% of people who take this drug chronically (98,99)

In patients with human immunodeficiency virus infection, it has been recommended to avoid the use of tenofovir when the glomerular filtration rate (GFR) is less than 60 mL / minute / 1.73 m², this is a strong recommendation in favor made by IDSA (Infectious Diseases Society of America). Likewise, in patients in whom a decrease in GFR greater than 25% from baseline or when it is less than 60 mL / minute / 1.73 m² has been confirmed, it is recommended to replace tenofovir, especially when there is evidence of proximal tubular dysfunction. (100)

Tenofovir has been infrequently associated with renal dysfunction due to tubular necrosis. Herlitz LC, et al., described 13 cases of tenofovir-associated nephrotoxicity: 6 women and 7 men with a mean age of 51.1 ± 9.6 years. Patients were treated with tenofovir for a mean of 19.6 months. Nine patients had acute kidney injury and 4 had mild kidney failure with sub nephrotic proteinuria. The mean serum creatinine was 1.3 ± 0.3 mg/dl, increasing to 5.7 ± 4.0 mg/dl at the time of the biopsy. Renal biopsy revealed acute toxic tubular necrosis. Clinical follow-up after tenofovir discontinuation averaged 13.6 months in 11 of the 13 patients. Recovery of kidney function occurred in all patients, including 4 who required temporary hemodialysis. The study showed that tenofovir disoproxil can lead to a form of reversible acute tubular necrosis. (101)

This effect in the reduction of GFR with the use of tenofovir seems to be related to the time of exposure to the drug and behaves as a reversible toxic damage, for which the timely withdrawal of the drug is indicated (102). During the clinical experiment, the intervention with tenofovir disoproxil is planned to be administered for 60 days, for which we estimate that this nephrotoxic effect will be very infrequent.

Cooper RD et al., In a systematic review and meta-analysis of 17 studies that included 9 randomized clinical trials and 7 prospective observational cohorts found that tenofovir was associated with lower creatinine clearance (averaging -3.9 ml / minute) compared to regimens without tenofovir (103). The studies included in the meta-analysis had a median follow-up of 48 weeks, and subjects with a GFR <50 or <60 ml/min/1.73 m² were excluded in 11 of them (102, 103).

Post marketing experience

Multiple adverse reactions have been described during post-approval use of TDF. No additional adverse reactions have been identified during use after FTC approval. These reactions are voluntarily reported by a population of uncertain size; Therefore, it is not always possible to establish causal relationships with drug exposure.

Among the adverse reactions that have been reported for TDF during surveillance are:

- o Immune system disorders: allergic reaction, including angioedema.
- o Metabolism and nutrition disorders: lactic acidosis, hypokalemia, hypophosphatemia.
- o Respiratory, thoracic, and mediastinal disorders: dyspnea

- o Gastrointestinal disorders: pancreatitis, increased amylase, abdominal pain.
- o Hepatobiliary disorders: hepatic steatosis, hepatitis, increased liver enzymes (most commonly AST, ALT)
- o Skin and subcutaneous tissue disorders: rash
- o Musculoskeletal and connective tissue disorders: rhabdomyolysis, osteomalacia (manifested as bone pain and may contribute to fractures), muscle weakness, myopathy.
- o Renal and urinary disorders: acute renal failure, renal failure, acute tubular necrosis, Fanconi syndrome, proximal renal tubulopathy, interstitial nephritis (including acute cases), nephrogenic diabetes insipidus, renal failure, increased creatinine, proteinuria, polyuria.

Most of the adverse events as described are mild and infrequent. Severe events are much rarer and most of them are dose dependent and occur with prolonged use of the drug. During the present study, the intervention time is short, which minimizes the risk of adverse events dependent on the prolonged use of TDF.

